3.5. Biomarkers

To date, no validated predictive marker has been identified in pancreatic neuroendocrine tumours. The importance of this research lies in being able to identify patients optimally to ensure as personalised a global approach as possible.

Although VEGF is considered to be the driving force behind angiogenesis in pNET, many studies have proven the involvement of other molecules such as PDGF, cKIT or mTOR. Initial data from patients with neuroendocrine tumours treated with sunitinib (33), (34) has been obtained by measuring circulating biomarker levels in the plasma, such as VEGF, soluble VEGF receptor-2 (sVEGFR-2), interleukin-8 (IL-8) and sVEGFR-3. In one of the studies, sVEGFR-2 and sVEGFR-3 levels dropped significantly by 30% after the first cycle, in 60% and 70% of patients, respectively. The reduction in sVEGFR-3 levels in the first cycle was greater in the subgroup of patients with partial response (N = 11). Elevated IL-8 levels were also identified in those patients with reduced tumour size.

Recently, a phase II study in pNET patients in first line or after progression and treated with pazopanib at a dose of 800 mg/24h, also included a biomarker expression analysis (35). Patients with some degree of VEGFR-2 expression tended towards longer PFS compared to those who did not express this protein (median 12.18 vs. 11.56 months; HR 0.95).

In 101 patients with a renal cell carcinoma treated with sunitinib, 16 SNPs (single nucleotide polymorphisms) have been evaluated, belonging to 9 genes that affect the pharmacodynamics [VEGFR2 (rs2305948, rs1870377), VEGFR3 (rs307826, rs448012, rs307821), PDGFR- α (rs35597368) and VEGF-A (rs2010963, rs699947, rs1570360) and IL8 (rs1126647), and pharmacokinetics [CYP3A4 (rs2740574), CYP3A5 (rs776746)], transport [ABCB1 (rs1045642, rs1128503, rs2032582) and [ABCG2 (rs2231142)] and metabolism [CYP3A5*1, CYP3A4] of sunitinib. The results defined a possible group of patients with VEGFR3 and CYP3A5*1 polymorphisms who had a lower response and worse tolerance to sunitinib (36).

The HIF-1 pathway is a crucial angiogenesis regulator involving other molecules such as VEGF, PDGF, angiopoietins (Ang-1 and Ang-2), DLL4 and metalloproteinases (37). Carbonic anhydrase (CAIX) is another factor associated with the activity of HIF-1 α and which regulates tumour pH and cell survival, together with cell adhesion. The expression of these key proteins in tumour hypoxia and their determination in pNET patients where this phenomenon is widely described, may contribute predictive information for incorporation in clinical practice.

Finally, TH-302 has been associated with hypoxia, which is why hypoxia markers (vascular microdensity, carbonic anhydrase IX, etc.) are potential candidates to predict which patients will be more likely to respond and which are not.

3.6. Rationale for the Clinical Development of this Study

NETs are highly vascular tumours exhibiting a high expression of proangiogenic molecules, such as VEGF. Many inhibitors of this pathway, such as monoclonal antibodies (bevacizumab) or tyrosine kinase inhibitors (sunitinib, sorafenib, pazopanib) have shown activity in pNET.

Despite these advances, a wider range of treatment options and the complexity of the treatment algorithm for pNET, the tumours may exhibit primary or acquired resistance after an initial response that make them insensitive to treatment with these drugs (38), (39).

Primary resistance to anti-angiogenic drugs may develop by the expression of proangiogenic factors that are relatively insensitive to VEGF-mediated inhibition (including c-MET, fibroblast growth factor (FGF), angiopoietins, and ephrins), or by the formation of blood vessels by other molecular pathways or the prior infiltration by inflammatory cells that express pro-inflammatory factors and cytokines that promote angiogenesis and which protect the blood vessel from VEGF-mediated inhibition. Acquired resistance may develop through the hypoxia-induced activation of alternative proangiogenic pathways such as angiopoietins, ephrins or FGF, or increase mesenchymal marker levels. These new receptors and molecular pathways seem to continue signalling through PI3K/AKT/mTOR (a finding that could potentially suggest secondary sensitivity to mTOR inhibitors), the recruitment of cells from bone marrow that contribute to VEGF-independent tumour vascularisation, pericyte-mediated protection or the invasion of non-tumour tissue with vessels that are more mature and less responsive to anti-VEGF therapy.

The mechanisms described that lead to an increase in the release of pro-angiogenic factors include accumulation of intratumoral HIF-1 α . (40).

In conclusion, pancreatic neuroendocrine tumours (pNET), which exhibit significant vascularisation, are sensitive to anti-angiogenic therapy, although with poor responses. In contrast, the chemotherapy regimens achieve a high objective response rate, although they are not sustainable over time. Therefore, the development of therapeutic targets against hypoxia, including reducible prodrugs, targets against HIF-1 and genetic engineering with anaerobic bacteria gives cause for optimism in overcoming resistance mechanisms of cell survival in hypoxic areas versus conventional chemotherapy.

Based on all the data presented above, the purpose of this study is to demonstrate the activity of TH-302 under hypoxic conditions, such as in neuroendocrine tumours, after sunitinib-induced response, which may be consolidated and prolonged to overcome an established resistance mechanism. The study shall try to determine the synergism and safety of this combination, in order to achieve improved and longer-lasting responses in unresectable, locally advanced or metastatic well- or moderately-differentiated pNET in first-line therapy.

4. STUDY OBJECTIVES

4.1. *Primary Objective*

Objective response rate (ORR).

4.2 *Secondary Objectives*

Progression-free survival (PFS)

Time to progression (TTP)

Response duration (RD)

Overall survival (OS)

Safety

Serological and tumour tissue biomarkers

5. STUDY DESCRIPTION

5.1. Design

This is a prospective, non-randomised, open-label, single-arm, phase II study that will assess the efficacy and safety of TH-302 plus sunitinib in patients with well- and moderately-differentiated metastatic pancreatic neuroendocrine tumours (pNET) who are naïve to systemic treatment other than somatostatin analogues. The study will include a serological biomarker analysis to investigate its clinically beneficial prognostic and predictive role.

The study will be conducted at 10 Spanish university sites belonging to the Spanish Task Force Group for Neuroendocrine Tumours (GETNE) network. GETNE will act as the study sponsor.

Once the patient has signed the informed consent form, he/she should be registered in the study, regardless of whether he/she meets the eligibility criteria, using the electronic data collection platform provided for the trial, at the following web address:

[REDACTED]

In the event that the patient meets all of the inclusion criteria and none of the exclusion criteria, an enrolment confirmation email will be sent with the corresponding patient number. The trial treatment may only be initiated once this confirmation has been received.

If any problems are detected with the tool during the enrolment process, or if the confirmation email is not received, please contact as soon as possible:

Marketing Farmacéutico & Investigación Clínica [Pharmaceutical Marketing & Clinical Research]

[REDACTED]

For more information concerning the enrolment procedure, please refer to the enrolment procedure available in the site's investigator files.

The tumour sample must be found and sent to [REDACTED] to perform the determinations detailed in this protocol. In addition, for patients who give their consent for the translational sub-study, blood samples (peripheral blood) must be collected prior to administration of the study medication and within the time limits defined in this protocol. These must be processed as laid out in section 8.1.

[figure not shown]
For more information about the shipment of the biological samples, please refer to the biological sample shipment procedure available in the site's investigator files.

The study treatment is TH-302, administered at doses of 340 mg/m² by intravenous infusion on days 8 and 22 in combination with sunitinib given orally at 37.5 mg per day continuously from day 1 through to day 28 of a 28-day treatment cycle. Patients will receive the study treatment until radiological progression is confirmed according to RECIST criteria version 1.1, or until treatment discontinuation is considered to be in the best interests of the patient, at the discretion of the investigator (these decisions will balance maximum benefit with acceptable tolerability). Patients will continue taking the study treatment at the discretion of the investigator should they experience clinical benefit.

A phase II trial to assess the activity and safety of TH-302 in combination with sunitinib in patients

Tumour response will be assessed every 8 weeks, regardless of any delay which may arise due to toxicity. To prevent the introduction of bias associated with treatment duration, compliance with the assessment schedule is essential.

5.2. Study Flow Chart

5.3. Study Duration and Schedule

Patient enrolment will take place over a period of 24 months, and a follow-up period of 20 months.

It is estimated that the study schedule will be as follows:

- Date of submission to central IEC for research with medicinal products: November:November 2014/January 2015.
- Data of submission/AEMPS approval: November 2014/January 2015
- Estimated date of enrolment of first patient: February 2015
- Study end date: January 2019
- Data analysis period: 4 months
- Database closure: April 2019
- Date for the final study report: June 2019
- Publication date: June 2019

5.4. Sample Size

It is estimated that a total of 43 eligible patients will be enrolled in the study (having received at least one dose of treatment). The design will follow *Simon's two-stage design* for phase II studies, with a baseline number of 18 patients. The combination of TH-302 with sunitinib will be considered as inactive in terms of the response rate if less than 5% of patients are responders, with a response rate threshold of 20%. These figures are based on the results shown with other drugs for the treatment of pNET.

A phase II trial to assess the activity and safety of TH-302 in combination with sunitinib in patients

Should a response be identified in at least 3 out of every 18 patients treated, recruitment will continue up to 43 patients in order to be able to better estimate the response rate. If the study shows a response in at least 8 patients, the treatment is likely to continue its research development.

The likelihood of terminating the study after the first part with 18 patients enrolled is 0.42 if the response rate is 10%, and 0.06 if the response rate is 25%.

The likelihood of not accepting the null hypothesis and considering the combination of TH-302 with sunitinib active with a response rate less than 5% is 5% (Type I or alpha error).

The likelihood of not rejecting the null hypothesis and considering the combination of TH-302 with sunitinib inactive with a response rate greater than 5% is 20% (Type II or beta error). The statistical power of the study will be 0.80.

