### 1.5.4. DETERMINATION OF SAMPLE SIZE

It is estimated that a total of 43 eligible patients will be enrolled in the study (having received at least one dose of treatment). The design will follow Simon's two-stage design for phase II studies, with a baseline number of 18 patients. The combination of TH-302 with sunitinib will be considered as inactive in terms of the response rate if less than 5% of patients are

responders, with a response rate threshold of 20%. These figures are based on the results shown with other drugs for the treatment of pNET.

Should a response be identified in at least 3 out of every 18 patients treated, recruitment will continue up to 43 patients in order to be able to better estimate the response rate. If the study shows a response in at least 8 patients, the treatment is likely to continue its research development.

The likelihood of terminating the study after the first part with 18 patients enrolled is 0.42 if the response rate is 10%, and 0.06 if the response rate is 25%.

The likelihood of not accepting the null hypothesis and considering the combination of TH-302 with sunitinib active with a response rate less than 5% is 5% (Type I or alpha error).

The likelihood of not rejecting the null hypothesis and considering the combination of TH-302 with sunitinib inactive with a response rate greater than 5% is 20% (Type II or beta error). The statistical power of the study will be 0.80.

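### The 3/18 then 8/43 rule does not have 0.80 power at the stated 20% response rate (it has 0.56), and the printed stage 1 stopping probabilities do not fit the rule

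*Protocol*

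**What the plan says.** Protocol 5.4 (Sample Size) sets out a Simon two-stage design.

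- **Hypotheses:** the combination is "inactive in terms of the response rate if less than 5% of patients are responders, with a response rate threshold of 20" percent. SAP 1.5.4 repeats this ("responders, with a response rate threshold of 20" percent).
- **Stage 1:** "Should a response be identified in at least 3 out of every 18 patients treated, recruitment will continue up to 43 patients".
- **Final rule:** "If the study shows a response in at least 8 patients", further development is likely.
- **Stage 1 stopping:** the probability of ending after 18 patients "is 0.42 if the response rate is 10%, and 0.06 if the response rate is 25" percent.
- **Type I error:** the chance of calling the combination "active with a response rate less than 5% is 5% (Type I or alpha error").
- **Type II error:** the chance of calling it "inactive with a response rate greater than 5% is 20% (Type II or beta error").
- **Power:** "The statistical power of the study will be 0.80".

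SAP 1.5.4 carries all of these statements, so the two documents agree with each other.

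**The concern.** One section uses two different pairs of response rates: 5% and 20% for the hypotheses, 10% and 25% for the stopping probabilities. A two-stage rule with fixed counts has one type I error at a given null rate and one power at a given alternative, so the printed figures can be checked against the printed rule. The type II sentence also ties 20% to every rate above 5%, although a type II error is defined only at a specific alternative.

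This rule is the trial's only formal decision on activity. If its stated properties are wrong, the sponsor does not know how likely it is to discard a useful combination. A reader of a positive result also cannot tell whether 8 of 43 is meant to exclude a 5% or a 10% response rate.

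**Working it through.** **Inputs (Protocol 5.4, SAP 1.5.4).** Stage 1 has 18 patients, with a stop at 2 or fewer responses. Stage 2 adds 43 − 18 = 25 patients. The result is positive at 8 or more responses in 43.

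**Formulas.** For true response rate p, with X the responses in the first 18 patients and Y those in the next 25:

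- P(stop at stage 1) = P(X ≤ 2 | 18, p)
- P(positive) = sum over x ≥ 3 of P(X = x | 18, p) × P(Y ≥ 8 − x | 25, p)

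**Step 1: do the stated alpha and power reproduce?**

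| True rate | P(stop at stage 1) | P(positive) |
|---|---|---|
| 5% | 0.942 | 0.0009 |
| 10% | 0.734 | 0.048 |
| 20% | 0.271 | 0.564 |
| 25% | 0.135 | 0.800 |

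At the stated 5% and 20% they do not: type I error is 0.0009 and power 0.564. At 10% and 25% they do: 0.048 and 0.800.

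The terms at 20%, for x = 3 to 7 and then x ≥ 8, are 0.1331 + 0.1649 + 0.1359 + 0.0794 + 0.0349 + 0.0163 = 0.5645. The chance of missing a true 20% rate is therefore 1 − 0.5645 = 0.4355, about 44%, against the stated 20%.

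**Step 2: could another final cut-off give 0.80 at 20%?** No. A positive result requires passing stage 1, and P(X ≥ 3 | 18, 0.20) = 1 − 0.2713 = 0.7287.

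**Step 3: which hypotheses does the rule fit?** A search for Simon's optimal design with alpha 0.05 and power 0.80 gives:

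- 10%/25%: stop at 2 or fewer of 18, negative at 7 or fewer of 43, which is the written rule exactly. Expected sample size at 10% is 18 + 25 × (1 − 0.7338) = 24.7.
- 5%/20%: stop at 0 of 10, negative at 3 or fewer of 29 (alpha 0.047, power 0.801). The minimax version is 0 of 13, then 3 of 27. Neither resembles the written rule.

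**Step 4: the stopping probabilities, at the rates the sentence itself names.**

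- 10%: P(0) + P(1) + P(2) = 0.1501 + 0.3002 + 0.2835 = 0.734 after rounding; stated 0.42.
- 25%: 0.0056 + 0.0338 + 0.0958 = 0.135 after rounding; stated 0.06.

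A cut-off slip does not explain the difference. With 18 patients, stopping at 1 or fewer gives 0.450 and 0.039, and stopping at 3 or fewer gives 0.902 and 0.306. Over stage 1 sizes 5 to 43 and stopping limits 0 to 7, no combination gives both 0.42 at 10% and 0.06 at 25% to within 0.006.

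**Step 5: the type II statement.** At a true rate of 10%, which is above 5%, the chance of a negative result is 1 − 0.048 = 0.952, not 0.20.

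**Step 6: if the stage 1 look is not taken.** The single-stage rule of 8 or more in 43 has probability 0.0012 at 5%, 0.061 at 10%, 0.650 at 20% and 0.876 at 25%. Dropping the look does not rescue 0.80 power at 20%, and it takes alpha above 5% for 10%/25%.

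**The case against.** The strongest reply is that the design is sound and only its labels are wrong. If 10%/25% was intended, alpha and power are as stated, the rule is clear and identical in both documents, and nothing changes in the conduct of the trial. That is plausible, and the exact match in Step 3 supports it. But neither document gives 10%/25% as hypotheses, and Protocol 5.4 says its 5% and 20% figures rest on results with other drugs. The stopping probabilities would still be wrong.

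Three narrower points have some force.

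- **The alpha discrepancy is conservative.** A type I error of 0.0009 respects a 5% ceiling, so it is not a breach. The cost falls on power.
- **The 20% figure is called a threshold, not an alternative.** Reading it as the alternative is natural in a Simon design, and no other candidate is stated alongside the 5%.
- **The stopping probabilities might be right for other rates.** Under the written rule, 0.06 is the stopping probability at a 30% response rate. But 0.42 would need a rate of about 16.3%, so the printed pair stays unexplained. What is certain is that the probabilities and the printed rates do not belong together.

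**Conclusion.** The concern holds, with high confidence. As written, the plan claims 0.80 power at a 20% response rate for a rule whose power there is 0.56 and cannot exceed 0.729. It also gives stage 1 stopping probabilities of 0.42 and 0.06 where the rule gives 0.73 and 0.14 at the same rates. The risk of stopping early on a combination with a true 25% response rate is more than twice the stated risk (0.135 against 0.06).

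The power result assumes that 20% is the alternative. The stopping result needs no assumption about the hypotheses. Both assume independent responses with a common rate, and a stage 1 look that is carried out as described. That 10%/25% was intended remains an inference.

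**What to change.** This must be corrected, in both Protocol 5.4 and SAP 1.5.4.

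1. **State one pair of hypotheses with matching figures.**
   - For 10%/25%: one-sided alpha 0.048, power 0.80, stage 1 stopping 0.73 at 10% and 0.14 at 25%, expected sample size 24.7 at 10%. The sentence justifying 5% and 20% by results with other drugs then needs a rationale for the new rates.
   - For 5%/20% with the present rule: type I error 0.0009, power 0.56, stage 1 stopping 0.94 at 5% and 0.27 at 20%.
   - The claim of 0.80 power at 20% cannot stand with the 3/18 requirement. Keeping that claim would mean a new rule and sample size.
2. **Remove 0.42 and 0.06.** At the rates now printed the values are 0.73 and 0.14.
3. **Tie the type II error to the chosen alternative**, not to all rates above 5%.

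Two related points should be settled at the same time. SAP 1.5.6 says no efficacy interim analysis of the primary endpoint is planned, which contradicts the response-based stop at 18 patients in SAP 1.5.4. The two-stage figures hold only if that look takes place. It would also help to say that the general two-tailed statement in Protocol 9.2 does not govern this one-sided count rule. At 8 of 43 the exact two-sided 95% interval is 8.4% to 33.4%, which excludes 5% but includes 10%.

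The cost is wording and figures in two sections, plus a reconciling sentence in SAP 1.5.6. Under either of the first two options patient numbers and cut-offs stay the same; the second obliges the sponsor to report power of 0.56.

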The PI3K/AKT/mTOR pathway is also key in tumour development, as it regulates the metabolism, growth, cell proliferation and angiogenesis, integrating multiple signalling pathways. Its activation can be responsive to VEGFR, PDGFR and insulin-like growth factor receptor (IGFR) stimulation, and it is regulated through two tumour suppressor genes (TSG) - TSC2 and PTEN. As everolimus deregulates this molecular pathway in pNET, use of the drug should be developed against these tumours. Thus, based on the phase II results published in 2008 with two cohorts of 60 patients treated with octreotide and everolimus at doses of 5 and 10 mg daily, a response rate of 27% was observed in pNET patients with a median PFS of 63 weeks (9). Based on these results, a second phase II study was developed, called RADIANT-1, targeting pNET patients who had progressed during or after chemotherapy and who received everolimus 10 mg/day, being stratified according to prior treatment with octreotide (115 patients in monotherapy and 45 patients in combination) (10). The results for both strata showed a response rate of 9.6% and 4.4%, respectively, and PFS was 9.7 vs. 16.7 months, respectively, for both arms. In a third phase III study, RADIANT-3, 410 pNET patients were randomised to receive everolimus 10 mg/day vs. placebo (11). The results of the study demonstrated significantly improved PFS with everolimus of 11.4 months versus 5.4 months (HR 0.34; $p < 0.0001$).

Unfortunately, patients ultimately progress and the development of new active drugs, as well as the development of predictive biomarkers of progression, is vital. The first study to analyse the sequence of therapeutic targets was the PAZONET study, the results of which were presented at ESMO 2012 (12). A total of 44 patients were enrolled who had previously received treatment with a tyrosine-kinase inhibitor (TKI) and/or mTOR inhibitor, and who were treated with pazopanib 800 mg/day allowing concomitance with somatostatin analogues. The results showed that pazopanib was active in this patient arm with a clinical benefit of 83% for those previously treated with TKI, 89% with an mTOR inhibitor and 60% with both drugs. The PFS in these three subgroups was 12.1 months, 6.8 months and 4.1 months, respectively. For the overall population it was 9.5 months.

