3.3. Sunitinib in Pancreatic Neuroendocrine Tumours

In pNET, there is a high expression of VEGF and VEGFR2-3, PDGFR alpha and beta, cKIT and EGFR, and hypoxia is a key event in the regulation of tumour angiogenesis. This constitutes a strong rationale when it comes to developing anti-angiogenic drugs for these tumours. In clinical studies, the activity of sunitinib on NET was first demonstrated in a phase I study where the 3 enrolled NET patients, all of whom had been previously treated, showed reduced tumour lesions to varying degrees, being exceptional in one patient with a higher partial response (21 weeks) and two long-lasting minor responses (13). Thereafter, a multicenter, phase II study was conducted in patients with carcinoid tumours and pNET (14). Results from the 66 pNET patients showed an objective response rate of 16.7% and a stable disease rate of 68%. The time to progression and overall survival at one year was 7.7 months and 81.1%, respectively. To definitively confirm this benefit, a phase III study versus placebo was developed, in which 171 patients of the 340 initially estimated were finally randomised against independent data monitoring (15). The benefit in terms of PFS was 11.4 months for the sunitinib arm at a dose of 37.5 mg/day versus 5.5 months for the placebo arm (HR 0.42; $p < 0.001$). Efficacy data on patients in routine clinical practice treated with sunitinib were consistent with those obtained on selected populations in clinical trials (16).

Figure 1. PFS results of the phase III study of sunitinib vs. placebo in pNET patients.

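### The 3/18 and 8/43 boundaries do not have the error rates stated for a 5% null and 20% target, the stage 1 stopping probabilities are wrong, and SAP 1.5.6 contradicts the stage 1 stop

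*Protocol*

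**What the plan says.** Protocol 5.4, repeated in SAP 1.5.4, calls the combination inactive below a 5% response rate and sets a 20% threshold. Alpha is 5%, attached to the 5% rate, and power is 0.80. Recruitment goes beyond 18 patients if at least 3 respond. At the end, "If the study shows a response in at least 8 patients, the treatment is likely to continue its research development". The source of the two rates is one sentence: "These figures are based on the results shown with other drugs for the treatment of pNET". No drug is named.

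The same section then gives the chance of stopping after 18 patients at a different pair of rates: it "is 0.42 if the response rate is 10%, and 0.06 if the response rate is 25" percent.

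SAP 1.5.6 states that no interim efficacy analysis of the primary endpoint is planned.

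Every patient receives sunitinib. The only sunitinib response rate in either document is in Protocol 3.3: "Results from the 66 pNET patients showed an objective response rate of 16.7% and a stable disease rate of 68" percent. For everolimus after chemotherapy, Protocol 3.2 reports: "The results for both strata showed a response rate of 9.6% and 4.4%, respectively". It also cites 27% for everolimus with octreotide.

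**The concern.** The section names two pairs of rates, 5%/20% and 10%/25%, for one set of boundaries. A rule with fixed boundaries has one alpha at each null and one power at each target, so both pairs cannot carry the stated 5% and 0.80. If the error rates do not belong to the boundaries, a reader cannot tell what a pass or a failure means.

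Two further matters affect how the result is read. Simon's design needs a look at the primary endpoint after 18 patients, and the SAP appears to exclude one. In addition, a null below the cited rate for a drug that every patient receives needs an explanation, because a pass leads to further development.

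**Working it through.** **Inputs.** From Protocol 5.4 and SAP 1.5.4: n1 = 18, continue at 3 or more; N = 43, positive at 8 or more; rates 5%/20% and 10%/25%. From Protocol 3.3: 16.7% of 66 patients. Only 11 responders fit that percentage (10/66 = 15.2%, 12/66 = 18.2%).

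**Formulas.** With X1 ~ Bin(18, p) and X2 ~ Bin(25, p) independent:

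- P(stop at stage 1) = P(X1 ≤ 2)
- P(pass) = Σ over x ≥ 3 of P(X1 = x) · P(X2 ≥ 8 − x)
- P(pass without the stage 1 stop) = P(Bin(43, p) ≥ 8)

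**The plan's own figures first.** P(stop) at 10% is 0.150 + 0.300 + 0.284 = 0.734, against the stated 0.42. At 25% it is 0.006 + 0.034 + 0.096 = 0.135 (rounded from unrounded terms), against 0.06. Lowering the gate by one response does not rescue them: P(X1 ≤ 1) is 0.450 and 0.040. With the 3/18 gate, 0.42 and 0.06 belong to true rates of about 16% and 30%.

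**Full rule:**

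| True rate | Stop at stage 1 | Pass, with the stop | Pass, without the stop |
|---|---|---|---|
| 5% | 0.942 | 0.0009 | 0.0012 |
| 10% | 0.734 | 0.048 | 0.061 |
| 15% | 0.480 | 0.258 | 0.313 |
| 16.7% (11/66) | 0.403 | 0.359 | 0.428 |
| 20% | 0.271 | 0.564 | 0.650 |
| 25% | 0.135 | 0.800 | 0.876 |

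At the stated 5%/20%, alpha is 0.0009, not 0.05, and power is 0.56, not 0.80. A regimen at the 20% threshold would be missed with probability 1 − 0.564 = 0.436. At 10%/25% the rule has alpha 0.048 and power 0.800.

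**Where the boundaries come from.** A search for Simon designs with alpha ≤ 0.05 and power ≥ 0.80 at 10%/25% returns these boundaries as the optimal design (stop at ≤ 2/18, negative at ≤ 7/43). At 5%/20% the optimal design is ≤ 0/10 and ≤ 3/29, and the minimax design is ≤ 0/13 and ≤ 3/27.

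**Effect of SAP 1.5.6.** If the stage 1 stop is not applied, the last column governs. Alpha at 10% is then 0.061, above the stated 5%, and power at 25% is 0.876.

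**What 8/43 shows.** 8/43 = 18.6%, exact 95% CI 8.4% to 33.4%. This excludes 5% and includes both 10% and 16.7%. The point estimate is 18.6 − 16.7 = 1.9 points above the cited sunitinib rate. That rate has its own exact 95% CI, 8.6% to 27.9% for 11/66. Over that interval the probability of passing runs from 0.02 to 0.88.

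**The case against.** Three objections have weight.

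**The intended pair of rates is an inference.** The section ties inactivity, alpha and beta to 5%; 10% and 25% appear only in the stopping sentence. The exact match to the optimal 10%/25% design makes that pair the likely source, but the documents do not say so. This stands: the sponsor has to confirm the rates.

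**The benchmark is weak.** A reader might infer that a 10% null is wrong and should have been 16.7%. The documents do not support that. 10% lies inside the interval for 11/66. Protocol 3.3 gives no line of therapy, schedule or confirmation rule for the 66 patients, and no response rate for the phase III sunitinib trial. The unnamed drugs could include everolimus. This stands too: what is missing is an explanation of the null, and the cited data do not show the null to be an error.

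**The plan already presents itself as a screen.** Protocol 5.1 says "This is a prospective, non-randomised, open-label, single-arm, phase II study", the listed objectives claim neither synergism nor superiority to sunitinib, and a pass only makes further development likely. A reader might infer from Protocol 3.6 ("the purpose of this study is to demonstrate the activity of TH-302 under hypoxic conditions"; "The study shall try to determine the synergism and safety of this combination") that the trial is designed to isolate TH-302 and fails to. No null could do that in a single arm, and this rationale text drives no analysis or decision rule. The wording is loose, but changing it is optional.

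None of this touches the arithmetic: the rates, boundaries and stopping probabilities in Protocol 5.4 and SAP 1.5.4 disagree.

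**Conclusion.** The inconsistency is real and appears in both documents. For the boundaries as written, alpha is 0.0009 and power 0.56 at the stated 5%/20%; the claimed 5% and 0.80 hold only at 10%/25% (0.048 and 0.80). The stopping probabilities are wrong at the rates they are quoted for: 0.73 and 0.14, not 0.42 and 0.06. SAP 1.5.6 conflicts with the stage 1 stop on which all the two-stage figures depend.

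A pass at 8/43 screens the combination against a low null. It does not show a response rate above that of sunitinib alone: a regimen with a true rate of 16.7% would pass with probability 0.36.

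The calculations assume independent responses with a common rate, all 18 and 43 patients counted in the denominator, and power read at the 20% threshold (the text attaches beta to any rate above 5%). The 0.36 also takes 16.7% as the true rate, which one study of 66 patients does not establish.

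**What to change.** Keep 18 and 43 patients and both boundaries.

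1. **Protocol 5.4 and SAP 1.5.4.** The sponsor confirms the intended rates and restates the figures to match. For 10%/25%: alpha 0.048, power 0.80, stage 1 stopping probabilities 0.73 and 0.14. If 5%/20% is kept: alpha 0.0009, power 0.56, stopping probabilities 0.94 and 0.27.
2. **SAP 1.5.6.** Name the assessment of the first 18 patients as a planned futility look on the primary endpoint. Without it, the figures in item 1 do not apply.
3. **Same sample-size sections.** Add one sentence explaining the chosen null against the cited 16.7% of 66 (exact 95% CI 8.6% to 27.9%). State that 8/43 screens the combination against that null and does not show a response rate above sunitinib alone.

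Optional: show the exact confidence interval for the response rate beside the 16.7% benchmark, as description only, and soften the wording in Protocol 3.6.

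The cost is text in both documents, with no extra patients and no change in the chance of passing. Either the stated null rises to 10% or the stated power falls to 0.56, and the claim attached to a pass becomes narrower. Because the SAP foresees a preliminary analysis with a 2017 data cut-off, the amendment should record its date relative to that cut-off.
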